HRV is a non-invasive surrogate measure of autonomic tone (the balance of the sympathetic and parasympathetic nervous systems), which is a critical determinant of outcomes in many cardiovascular conditions.^{59, 60} This analysis will offer insight into mechanisms responsible from a neuromodulatory perspective. A 15-minute single-lead reading will be performed including at rest and after randomization arms, with an ~5 minute segment exported for analysis (e.g. Kubios HRV software). This analysis will only be performed in participants in sinus rhythm. We will measure standard indices in HRV analysis (including time- and frequency-domain indices). The principal index will be standard deviation of the N-N (R-R) intervals. We may also assess high frequency and low frequency power, as well as their ratio.

Potential Pitfalls and Troubleshooting Strategies

Absorption of the compound is brisk and results in serum BHB levels of roughly 3 mmol/L in healthy volunteers at the dose studied here. Among HF patients, gut absorption might be reduced or delayed, leading to different peak effects of the compound. To address this potential problem, we have used a moderate dose of the compound to ensure we achieve therapeutic ketosis. Even if our goal levels of serum BHB are not achieved, recent data has demonstrated the benefits of ketone therapy accrue at even low levels (<1 mmol/L).⁶¹

Risks and Safety Assessment

KE risks: Rigorous previous analysis of the compound at doses (714 mg/kg) greater than what is administered here revealed a very favorable safety profile when administered as a single dose, with only 1 adverse event reported (transient mild rise in triglycerides that resolved by study completion). While ketoacidosis can induce pH disturbances or neurologic complications, this is seen only at supraphysiologic levels (10-20 mmol/L); our study is anticipated to achieve levels of around 3 mmol/L, similar to the levels observed with fasting for a few days (for example, levels of roughly 2 mmol/L are achieved after 48 hours of fasting). We are also excluding type 1 diabetics, who are at risk of ketoacidosis for other reasons as well as those on SGLT2 inhibitors which can lead to ketoacidosis as well. Given that type 2 diabetics are not generally at risk for diabetic ketoacidosis, we will include

them in our study. Vital signs will be monitored closely during the study visits. Documentation of adverse event monitoring will take place during the study. Given the short half-life of the compound, adverse events will be considered up to the time of the participant leaving the research unit.

We will also review the medical charts of patients with an implantable cardioverter-defibrillator to determine therapy zones prior to exercise. The primary safety outcome will be stress-induced sustained arrhythmias during exercise (atrial arrythmias, ventricular tachycardia). Participants are free to terminate study involvement at any time, at which time they may be asked the reason for study termination.

Stable Isotope Infusion [(6,6-²**H**₂**)glucose]:** There are no known risks associated with the use of stable isotopes as proposed in this study.⁵¹ Stable isotopes are not radioactive. Solutions will be prepared by UPenn IDS and will be tested for sterility and the absence of pyrogens.

References

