We now have a unique opportunity to study a nutraceutical ketone ester (**KE**), (R)-3-hydroxybutyl (R)-3-hydroxybutyrate (commercially known as "DeltaG"), that provides systemic ketosis in a deep phenotyping study of HFpEF patients.⁹ Initial studies of DeltaG demonstrated significant improvement in exercise capacity among endurance athletes.¹⁰ Because exercise limitation is a cardinal feature of HF, KE therapy has the potential to likewise improve exercise capacity in HFpEF.

Our **Specific Aims** and **Hypotheses** are as follows:

Aim 1. To determine the acute effects of single dose DeltaG administration on maximal (peak VO₂) and submaximal exercise capacity (exercise time) assessed by cardiopulmonary exercise testing (CPET) among patients with HFpEF.

Hypothesis: DeltaG will improve peak VO₂ and submaximal exercise time compared to a matching placebo.

Subaim 1. To determine the impact of DeltaG on metabolic and biomarker profiles during exercise.

Hypothesis: DeltaG will reduce lactate production during exercise.

- Aim 2. To assess the effects of DeltaG on cardiovascular hemodynamics during exercise.

 Hypothesis: DeltaG will reduce systemic vascular resistance as well as demonstrate improvements in cardiac output at peak exercise compared to placebo.
- Aim 3. To profile the effects of ketone ester versus placebo on systemic and plasma carbohydrate metabolism during exercise using indirect calorimetry and stable isotopes (²H-glucose) techniques *Hypothesis: Delta G will reduce systemic carbohydrate utilization at steady-state during submaximal exercise, with concordant reductions in plasma glucose oxidation*

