3. BACKGROUND AND SIGNIFICANCE

HF affects 6.2 million Americans and is associated with substantial morbidity and mortality in the contemporary era.¹ By 2030, the burden of HF is anticipated to surpass 8 million with an associated economic toll of a staggering \$69.8 billion.¹ The cardinal clinical feature of patients with HF is reduced exercise capacity, which is associated with a substantial reduction in quality of life.¹¹ Despite significant advancements in therapy for patients with HF, particularly among those with reduced ejection fraction (EF), many still suffer from limitations in exercise capacity and a poor prognosis. As such, exploring other avenues to reduce morbidity from HF is of vital interest from societal, economic, clinical, and patient-centered perspectives.

Ketone bodies (acetoacetate, β-hydroxybutyrate [BHB], and acetone) are water-soluble molecules produced from acetyl-CoA following breakdown of fatty acids (and amino acids) mainly in hepatic cells. Ketone bodies are typically absent from the circulation during the normal fed state, but are produced continuously during metabolic stress conditions and/or periods of carbohydrate deprivation such as acute medical stress, prolonged exercise, or starvation, and become a key source of energy to vital organs including the brain and heart under these circumstances. Let Ketone production has long been teleologically considered as a means to provide the brain with an efficient, alternative fuel source during starvation, sparing carbohydrate and protein stores, since the brain cannot effectively metabolize free fatty acids (which represent 99% of the body's energy stores). When completely oxidized in the citric acid cycle, ketones have a respiratory quotient similar to glucose (acetoacetate = 1.0, BHB = 0.89) and produce greater amounts of ATP, releasing approximately 30% more energy per molecule than pyruvate. The liver produces ketone bodies from mobilized fat stores that then can be utilized by neural tissue to produce ATP. It is therefore not surprising that several neurologic

diseases have been treated, or are under study, with ketone therapy, such as epilepsy, Parkinson's disease, and Alzheimer's disease. 16

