Concentrations of the KE compound of roughly 3-5 mmol/L are reached within 60 minutes at doses studied here.^{9, 10} The half-life of the compound is 0.8-3.1 hours.⁹ The KE compound has a very favorable safety profile with adverse effects limited to dose-dependent, gastrointestinal distress that typically occur only at the highest levels of administration (714 mg/kg).^{9, 35}

5. Research Design and Methods

Overview: The overall study design will be a randomized, double-blind crossover comparison of DeltaG therapy vs. KE-free vehicle in 20 patients with HFpEF. The main outcomes will be measures of exercise performance (peak and submaximal exercise) and associated metabolic and cardiovascular metrics. The CHPS will provide many study services requested through a Doris Duke Charitable Foundation award (to SS).

The overall structure include 3 visits:

• 3 Visits during which cardiopulmonary exercise testing will be performed (and related testing at these visits), with 1 baseline visit and 2 exercise endpoint assessment visits.

Study population (Inclusion criteria)

Participants aged 18-85 years of age, stable medical therapy for 2 weeks, and New York Heart Association (NYHA) class II or III will be included for this study. We will recruit 20 HFpEF participants. Participants will be recruited from UPHS enterprise. Given the challenges of the diagnosis of HFpEF, and to include a more homogenous cohort, we have the following inclusion criteria:

- 1. Left ventricular ejection fraction ≥ 50%
- 2. Evidence for elevated filling pressures as follows (at least one of the following between a-d):
 - a. Mitral early (E)/mitral septal tissue annular (e') velocity ratio > 8 in addition to one of the following:
 - i. Large left atrium (LA>4.0 cm width or LA volume index >34 mL/m²)^{36, 37}
 - ii. Chronic loop diuretic use for control of symptoms
 - Elevated natriuretic peptides within the past year (NT-proBNP>125 pg/ml or BNP>35 pg/ml)
 - b. Mitral E/e' ratio > 14^{37} at rest or with exercise
 - c. Elevated invasively-determined filling pressures previously (resting left ventricular end-diastolic pressure ≥16 mm Hg or pulmonary capillary wedge pressure ≥ 15 mmHg; or PCWP/LVEDP ≥ 25 mmHg with exercise)³⁸
 - d. Prior episode of acute heart failure requiring IV diuretics with evidence of volume overload on exam/radiology or elevated natriuretic peptides.

Exclusion Criteria

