Blood samples will be stored at -80C for later analysis. We may perform comprehensive metabolomic profiling from this peripheral blood, in addition to other tests.

Table 2. Timing of Laboratory Draws during Study Protocol for Visit 2 and 3 WITHOUT Stable Isotope Infusion

Study Time	Plasma and/or Serum Tube Draw
0-30 minutes (baseline)	Х
60 minutes (intervention given) – blood draw immediately before intervention	X
90 minutes (start of echo)	X

105 minutes (mid-echo)	Х
120 minutes (start of maximal effort exercise)	Х
Every 3 minutes during maximal effort exercise	Х
Standardized draw at 25 Watts (if not already drawn)	Х
Time of exhaustion after maximal effort exercise	Х
Following 15 minutes of rest after completion of peak VO ₂ study recovery and prior to lunch	Х
~160 minutes (1/2 dose of intervention prior to submax CPET – blood draw immediately prior to intervention)	X
~190 minutes (submaximal CPET): At rest, 4 minutes (standardized draw), and time of exhaustion	Х

Total blood drawn at Visit 2 and 3: ~180 mL/visit

Stable Isotope Infusion

A secondary goal of this proposal is to understand the metabolic changes induced by acute ketone administration. As described above, ketones have been shown to reduce glucose utilization in both healthy 10, 24, 44 and disease populations. 45 Systemic substrate utilization can be estimated through indirect calorimetry, using the data from gas exchange (carbon dioxide production rate and oxygen uptake rate) to derive rates of systemic carbohydrate and fatty acid oxidation. 46, 47 Yet systemic measurements do not identify the source of the substrate utilized (i.e. plasma-derived versus intramuscular), which may vary with exercise intensity, gender, and possibly disease state. 48-50 Knowing whether there is a deficit in substrate import, leading to alterations in utilization, could lead to new therapeutic opportunities.

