Stable isotopes, in which the molecular weight of an atom is slightly increased due to additional neutrons within the nucleus, are naturally-occurring, non-radioactive, and are handled similarly by the body to their more abundant counterparts.⁵¹ The higher molecular weight of the compound allows this 'label' to be traced throughout the body and the plasma using mass-spectometry. When infused into the blood, rates of endogenous production and utilization can be computed. Comparison of systemic oxidation rates with those derived from plasma measurements allows for an estimation of oxidation rates from intramuscular stores.⁴⁸

To define how exogenous ketones affect endogenous glucose utilization, we may infuse [6,6-²H₂] glucose during the submaximal exercise in a subset of participants. Participants will be administered stable isotope pending ability to place a second, contralateral IV. In such cases, infusions will be started ~1.5 hour prior to submaximal exercise, and initiated with a 5 mg/kg priming dose (MW 182.17 g/mole; 27.45 umol/kg; delivered over 5 minutes) followed by a continuous infusion at 0.05 mg/kg/min (0.2745 umol/kg/min), leading to a 100:1 prime/continuous infusion ratio.⁵² We note that this prime/infusion protocol is well established and is used on campus by other investigators.⁵³ The stable isotope will be infused intravenously, with sampling done from a peripheral vein on the contralateral extremity. A typical blood sampling schema may be as follows: (a) prior to start of infusion, (b) every ten minutes following the start of the continuous infusion, (c) densely around 1 hour after delivery of the prime and start of the continuous infusion (for example, at 55, 60, and 65 minutes), (c) every ten minutes following administration of the study intervention and immediately prior to the start of exercise, (d) every 2 minutes during exercise, (e) at the time of exhaustion, (f) every 2 minutes during recovery for 10 minutes (Table 3). Plasma samples will be stored for later mass-spec analysis. Additional blood samples may also be taken. It is anticipated that the addition of stable isotopes to the submaximal study will only require ~30 mL/ of additional blood/endpoint assessment visit, as mass spectrometry measurements can be made on a small volume (<2 mL).

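### Systemic carbohydrate use is inferred from gas exchange with no ketone term, so extra ketone oxidation at the ketone visit is partly counted as carbohydrate and can mask the sparing effect that Aim 3 looks for

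*Protocol*

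**What the plan says.** - **Protocol, section 2, Aim 3.** The hypothesis is that the ester will "reduce systemic carbohydrate utilization at steady-state during submaximal exercise". Indirect calorimetry is one of the two techniques named for the aim.
- **Protocol, section 5, Stable Isotope Infusion.** Systemic substrate use is estimated by taking VCO₂ and VO₂ "to derive rates of systemic carbohydrate and fatty acid oxidation". Two gases are measured and two fuels are named. The same section adds: "Comparison of systemic oxidation rates with those derived from plasma measurements allows for an estimation of oxidation rates from intramuscular stores".
- **Protocol, section 3.** On complete oxidation, "ketones have a respiratory quotient similar to glucose (acetoacetate = 1.0, BHB = 0.89".
- **Protocol, section 4.** The ester splits into BHB and butanediol, and the liver turns the butanediol into more BHB. "The half-life of the compound is 0.8-3.1 hours".
- **Protocol, Risks and Safety Assessment.** On blood BHB, "our study is anticipated to achieve levels of around 3 mmol/L".
- **Protocol, CPET Study Design.** Endogenous ketones supply 2-6% of energy needs after an overnight fast.
- **SAP, Secondary and Exploratory Endpoints.** Peak RER in the maximal test is a secondary endpoint, presented as reflecting substrate utilization. RER is exploratory at 25 W, at peak, at 4 minutes of the submaximal test and at exhaustion. Glucose appearance and disappearance are listed for the isotope subgroup. No systemic carbohydrate or fat oxidation rate is listed.

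Neither document describes a ketone correction, a caveat or a sensitivity analysis for these quantities.

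**The concern.** The intervention supplies a third fuel, mainly at one of the two visits being compared. Its RQ lies between those of fat and carbohydrate, or equals that of carbohydrate. A calculation that knows only carbohydrate and fat must assign ketone oxygen to those two, and part of it goes to carbohydrate. Because this differs by treatment, the crossover does not cancel it.

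Taken alone, the error adds apparent carbohydrate at the ketone visit, against the direction that Aim 3 predicts. A true fall would look smaller. A null result, or a higher RER on ketone, could be written up as no carbohydrate sparing when the data cannot show that. An intramuscular estimate built from the systemic rate would carry the same error.

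**Working it through.** **Inputs from the documents:** RQ 0.89 for BHB and 1.0 for acetoacetate; BHB about 3 mmol/L; half-life 0.8-3.1 h.

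**Assumptions:** fat RQ 0.7 (0.69-0.71 tried); carbohydrate RQ 1.0 (glucose); placebo RER 0.95; extra ketone share of VO₂ *k* = 10%; equal total VO₂ at the two visits. The documents give no ketone share during exercise.

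**1. The protocol's RQs.** RQ = C/(C + H/4 − O/2).
- BHB (C₄H₈O₃): 4/4.5 = 0.889, stated as 0.89.
- Acetoacetate (C₄H₆O₃): 4/4 = 1.0, as stated.
- Whole ester (C₈H₁₆O₄), including the butanediol step: 8/10 = 0.80. The protocol does not give this figure.

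The ester yields BHB, and acetoacetate is formed from BHB, so 1.0 is best read as an upper bound.

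**2. Part of ketone oxygen booked as carbohydrate.** s = (RQ − 0.7)/0.3.
- RQ 0.80: 0.10/0.3 = 33%
- RQ 0.89: 0.19/0.3 = 63% (62-65% for fat RQ 0.71-0.69)
- RQ 1.0: 0.30/0.3 = 100%

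**3. Effect on the contrast.** Placebo carbohydrate share = (0.95 − 0.7)/0.3 = 83.3% of VO₂; fat = 16.7%. If ketones displace both in proportion, true carbohydrate use falls by 10% and ketone-visit RER = 0.9 × 0.95 + 0.1 × RQ.

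| Ketone RQ | Ketone-visit RER | Apparent carbohydrate share | Apparent change (true −10%) |
|---|---|---|---|
| 0.80 | 0.935 | 78.3% | −6.0% |
| 0.89 | 0.944 | 81.3% | −2.4% |
| 1.0 (bound) | 0.955 | 85.0% | +2.0% |

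**4. When the sign reverses.** If a fraction *c* of ketone use displaces carbohydrate, the true change is −kc and the apparent change is k(s − c), both in share of VO₂. The sign flips when c < s. For BHB, more than 1 − 0.633 = 37% of ketone use must displace fat; at RQ 0.80, more than 67%. Under proportional displacement the sign flips only if placebo RER is below the ketone RQ, so below 0.89 for BHB.

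**5. Is 10% plausible?** Assume a distribution volume of 0.3 L/kg, submaximal VO₂ of 10 mL/kg/min, and elimination wholly by oxidation (4.5 mol O₂ per mol BHB, 22.4 mL per mmol). Ketone VO₂ = 3 × 0.3 × ln 2/(60 × half-life in hours) × 4.5 × 22.4.
- Half-life 0.8 h: 1.31 mL/kg/min, or 13% of VO₂.
- Half-life 3.1 h: 0.34 mL/kg/min, or 3%.

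With volume 0.2-0.5 L/kg and VO₂ 8-14 mL/kg/min the range is about 2-27%.

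**6. What a correction does.** Corrected carbohydrate share = [RER − k·RQ − 0.7(1 − k)]/0.3. For the RQ 0.89 row: (0.944 − 0.089 − 0.63)/0.3 = 75.0%, which is 10% below 83.3%, so the true fall is recovered. If *k* and RQ are unknown, the same RER of 0.944 gives −2.4% at k = 0, −8.4% at k = 15% with RQ 0.80, and −20.4% at k = 15% with RQ 1.0.

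**The case against.** Several points on the other side stand.

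- **The SAP lists RER, not oxidation rates.** The protocol's remarks on systemic and intramuscular oxidation describe a method, and its equations are not printed. Two-fuel use is inferred from the named outputs and the absence of a ketone term. The concern remains because Aim 3 is framed as carbohydrate use and the SAP ties RER to substrate utilization.
- **The error is not confined to the ketone visit.** By the protocol's own 2-6% figure, some ketone is oxidised after an overnight fast without the drink. Only the excess on ketone biases the contrast.
- **BHB alone may overstate the error.** Counting the butanediol step lowers the RQ to 0.80, with the same sign and a smaller size.
- **Another bias may oppose this one.** The submaximal test is titrated to exhaustion in about 3 to 6 minutes, and Subaim 1 expects less lactate on ketone. Less buffering CO₂ would lower ketone-visit RER.

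A reader might infer that Aim 3 will come out reversed. The documents do not support that: in the example with RQ 0.80 or 0.89, proportional displacement gives attenuation only. Nor can a 20% share displacing fat alone serve as an illustration at RER 0.95, because fat is then only 16.7% of VO₂.

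**Conclusion.** The point holds as a problem of interpretation. Without a ketone term, extra ketone oxidation adds apparent carbohydrate at the ketone visit. In the example, a true 10% fall is seen as 2.4% (RQ 0.89) or 6.0% (RQ 0.80). These figures rest on fat RQ 0.7, placebo RER 0.95, a 10% extra ketone share and proportional displacement. The first needs only slight variation; the other three are not given in the documents. Reversal is possible but conditional.

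This component has a known direction, but the net bias in RER does not, because buffering CO₂ may oppose it. It would also go too far to infer that Aim 3 as a whole, or the trial's main result, is compromised. Tracer glucose appearance and disappearance do not depend on RQ, though they cover only a subgroup, and neither co-primary endpoint uses substrate partitioning. What the plan cannot support is reading a null or raised RER, or carbohydrate rate, as absence of sparing. The SAP should deal with this.

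**What to change.** Add a paragraph to the SAP:

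1. Report RER differences as RER. Do not label them carbohydrate use or substrate utilization on their own.
2. Wherever carbohydrate or fat oxidation, or an intramuscular estimate, is reported, also compute it after removing ketone O₂ and CO₂. Use a stated range of excess ketone share (for example 0-15% of VO₂, limited so that fat stays non-negative) and of ketone RQ (0.80-1.0), and present the whole range.
3. A fall in the uncorrected (0%) analysis may be called conservative with respect to this bias only.
4. Do not report a null or a rise as absence of carbohydrate sparing unless it persists across the whole range.

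The work is a short sensitivity calculation on gas-exchange data already planned, with no new visits or samples. The price is a less definite answer, because ketone oxidation itself is not measured and the carbohydrate result becomes a range. Rule 4 is demanding: at placebo RER 0.95, a 15% share at RQ 1.0 removes 0.15/0.833 = 18% of placebo carbohydrate use, so an uncorrected null will usually end as inconclusive. That is an accurate statement of what gas exchange alone can show here.

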[figure not shown]

Acute Effects of Exogenous Ketone Ester Administration in Heart Failure

Statistical Analysis Plan

ClinicalTrials.gov Identifier: NCT04633460

Date: February 1st, 2024

[name]

[name], ScD

Study Design: Two-sequence, two-treatment individual-randomized crossover design.

Description of Baseline Characteristics: The demographic and clinical characteristics of the sample will be described overall (intention-to-treat) and by arm using descriptive statistics (means, medians, percentages) with measures of the variation (standard deviation (SD) and interquartile range (IQR)). Graphical procedures will be used to assess distributional assumptions.

Primary Analysis: The primary analysis will regress the difference in outcome for ketone versus placebo on treatment sequence. A Wald test of the intercept will be used for the hypothesis test of a treatment effect. The two co-primary outcomes are:

1. Peak VO_2 during incremental (maximal) exercise testing
2. Time to exhaustion during submaximal exercise testing at 75% peak workload

A type I error rate of 0.05 is pre-specified without correction for multiple comparisons.

Secondary Endpoints: The secondary outcomes will be analyzed using the same model. These are:

1. Percent change in systemic vascular resistance with maximal exercise testing at peak
2. Substrate utilization (reflected by the respiratory exchange ratio) during maximal exercise testing at peak
3. VO_2 efficiency (the ratio of total work performed over oxygen consumed above baseline during exercise, kJ/L of O_2) during submaximal cardiopulmonary exercise testing.

Exploratory Endpoints: Exploratory outcomes will be used to further understand possible mechanisms of action for the change in primary and secondary outcomes, and include several domains:

- (a) Resting echocardiographic data: left ventricular ejection fraction, peak left ventricular global longitudinal strain, e' septal and lateral velocity, E/e' ratio, tricuspid annular planar systolic excursion, and the right ventricular s' velocity.
- (b) Exercise hemodynamic data: Cardiac Output (heart rate x stroke volume), VE/VCO_2 slope, the arteriovenous O_2 content difference (quotient of VO_2 to cardiac output), mean arterial pressure, the vasodilatory reserve, and the mitral E to septal e' ratio assessed at:
 - 25 watts of exercise during incremental study
 - Peak of the incremental study
 - 4 min during the submaximal study
 - Time of exhaustion during the submaximal study
- (c) Exercise metabolic data:
 - Ventilatory Threshold (using the average of the V-slope method and the Ventilatory Equivalents method, when available)
 - Respiratory Exchange Ratio assessed at:
 - 25W of exercise during incremental study
 - Peak of the incremental study
 - 4 min during the submaximal study
 - Time of exhaustion during the submaximal study
 - Beta-hydroxybutyrate, glucose, lactate, non-esterified fatty acids, insulin, and glucagon assessed at:
 - 25W of exercise during incremental study
 - Peak of the incremental study
 - 4 min during the submaximal study
 - Time of exhaustion during the submaximal study

- Glucose kinetics during the submaximal study in the subgroup who received stable isotopes during the intervention visits:
 - Glucose rate of appearance
 - Glucose rate of disappearance

Safety Endpoint: Presence of exercise-induced arrhythmias (significant atrial or ventricular arrhythmias)

Physiologic Response to the Intervention: In addition to the primary and secondary outcomes, multiple other physiologic endpoints were collected, with some at multiple timepoints within each visit. For some endpoints, not all measurements occurred at regular intervals, and the number of measurements per subject varied. These analyses will be analyzed similarly to the primary endpoints, but with changes to address the repeated measurements within visits. In some cases, the responses can be summarized using a single summary statistic, e.g. the area under a curve (AUC) or the initial slope, while in other cases the individual measurements are of interest. Mixed effects models may be employed to efficiently answer questions related to outcome variables with repeated measurements.

Subgroup analyses:

- Biological sex
- Baseline peak VO_2 indexed to body weight (above versus below median value)
- Diabetic status (No versus Yes)
- Left ventricular ejection fraction above and below 60%¹

A term for subgroup will be included in the model described above. A Wald-test of significance will be used to compare to the null value. This analysis is equivalent to the interaction analysis used in the analysis of parallel-group designs. Results will be presented graphically in a forest plot. Subgroup analyses are considered exploratory and thus no formal corrections for multiple comparisons will be used. Rather across the two primary outcomes, and with 4 subgroups, the expected number of tests with a p-value less than 0.05 is 0.4 hypothesis tests. More than one test with $p < 0.05$ is suggestive of treatment effect heterogeneity.

Hypothesis generating analysis:

The achieved level of ketone in blood immediately prior to exercise is hypothesized to relate to each of the primary outcomes. This hypothesis will be explored graphically and using linear regression models with stratification by treatment sequence.

Power Calculations for Primary Endpoints:

Peak VO_2 : With 18 subjects (9 per treatment sequence), the study has 91% power to detect a mean difference in peak VO_2 (mL/min/kg) between ketone and placebo of 1 mL/min/kg (effect size=0.83), assuming a standard deviation for the difference of 1.2 mL/min/kg.² The power calculation is based on a paired t-test with a two-sided type I error rate of 0.05.

Submaximal Exercise Endurance: Using the effect size noted in a study examining the impact of inorganic nitrate on submaximal exercise endurance in HFpEF,³ a sample size of 18 participants has 88% power to detect an effect size of 0.78, using a paired t-test with a two-sided type I error rate of 0.05, assuming a correlation of 0.8 between measurements on the same individual.

A total of 21 participants were randomized anticipating loss to follow-up of around 3 participants (14%).

References

